## Background and Rationale

Cytomegalovirus DNAemia occurs frequently in allogeneic hematopoietic stem cell transplant (allo-HSCT) recipients [1]. Both high-level and persistent virus DNAemia are known risk factors for CMV end-organ disease and perhaps non-relapse mortality [2]. CMV DNAemia is usually documented after engraftment, but it may occur before. The virological features and clinical consequences of these latter early-onset episodes remain largely unexplored. The U.S. Food and Drug Administration (FDA) has recently approved letermovir for prophylaxis of CMV infection and disease in adult CMV-seropositive allo-HSCT recipients (PREVYMIS™, Merck & Co., New Jersey, USA). In accordance with the design of the phase III, double-blind trial [3] the drug may be administered as early as the day of transplant and no later than 28 days post-transplant. Nevertheless, the timing of drug inception should be contingent on the clinical impact of very early episodes of CMV DNAemia. In a recent work from our group (single-center study) [4] we found that a total 38 out of the 197 patients in our series developed CMV DNAemia before engraftment (cumulative incidence, 19%; 95% CI, 10-30.3%). Nine episodes of CMV DNAemia were detected prior to the time of donor progenitor cell infusion. A greater number of post-engraftment episodes required preemptive antiviral therapy compared with pre-engraftment episodes (62.5% vs 44.7%;  $P=0.05$ ). The cellular content of the donor progenitor cell infusion and transplant characteristics of patients did not differ between patients with pre- or post-engraftment CMV DNAemia. The cumulative incidence of overall mortality by days 100 and 365, aGVHD by day 100 and relapse by day 365 were not significantly different between patients with pre-engraftment or post-engraftment CMV DNAemia. Our study was limited by the retrospective and single-center design and the scarce number of pre-engraftment CMV DNAemia episodes included; therefore, the results may not be extrapolated to other transplantation centers or patient cohorts. Further retrospective and prospective studies are thus required to validate the data presented herein.

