## Objectives

**1. Assess the incidence of pre-engraftment CMV DNAemia using highly sensitive real-time PCR assays in allo-HSCT**

**2. Evaluate its impact of pre-engraftment CMV DNAemia on the time to engraftment, overall mortality, and non-relapse mortality.**

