### **Hypothesis**

**Very early episodes of CMV DNAemia have no impact on the occurrence of engraftment, overall mortality and non-relapse mortality.**

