### **Study Design/Clinical Plan**

This is a multicenter, retrospective, observational and single arm study which will include all consecutive allo-HSCT recipients at risk of CMV infection allografted from 1st January 2010 until 31th December 2019 in Spanish transplant centers belonging to the “Grupo Español de trasplante hematopoyético y terapia celular” (GETH group). No less than 10 centers performing bot related and unrelated allo-HSCT in Spain will participate in the study.

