**Analysis of the clinical impact of CMV DNAemia will be performed by evaluation of:**

- Time to engraftment
- Overall mortality

The analysis will be performed comparing the clinical impact of CMV DNAemia as described before, in relation to time of CMV DNAemia initiation in the following groups:

- Patients with DNAemia before engraftment vs after engraftment
- Patients with DNAemia before engraftment and before HSC infusion vs patients with DNAemia before engraftment after HCS infusion
- Comparison of time of initiation of CMV DNAemia from day -7 to HCS infusion on a weekly basis until engraftment.

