## Statistical Plans

**Non-parametric and semi-parametric analyses.** The probabilities of CMV DNAemia, CMV DNAemia requiring pre-emptive therapy, CMV-D, NRM and relapse will be estimated by the cumulative incidence method (marginal probability).

Competing events will be defined as follows; in the case of relapse, the competing event was NRM without the occurrence of the disease. For CMV DNAemia, CMV DNAemia requiring pre-emptive therapy, CMV-D and GVHD the competing event will be relapse or death without the event. For NRM the competing event will be relapse.

The assumption of proportional hazards over time will be tested for all explanatory covariates using a time-dependent covariate. CMV DNAemia, CMV DNAemia requiring pre-emptive therapy and CMV-D will be treated as time-dependent co-variates.

If time-dependent covariates are to be included in the final model multivariate analyses of mortality the analysis will be performed by Cox proportional hazards regression model, with inclusion of those variables with a P value less than 0.1 in the prior univariate testing.

If either, early or late CMV DNAemia (included individually as time-dependent covariates) are found to have an impact on OS in the univariate analysis, semi-landmark plot will be constructed to illustrate visually the effect.

Statistical analysis of the clinical impact of CMV DNAemia at different periods of time before engraftment will be performed as described previously for early or late CMV DNAemia

All statistical analyses will be performed using SPSS version 20 (SPSS, Chicago, IL) and R version 2.12.2 (The CRAN project) with the packages survival v2.36-10, Design 2.3-0, prolim v1.2.1 and cmprsk v2.2-221.

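### The hypothesis needs pre-engraftment DNAemia compared with no DNAemia, and no analysis in the plan reliably makes that comparison

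*Combined protocol and SAP*

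**What the plan says.** The Hypothesis section states: "Very early episodes of CMV DNAemia have no impact on the occurrence of engraftment, overall mortality and non-relapse mortality". Objective 2 matches it: "Evaluate its impact of pre-engraftment CMV DNAemia on the time to engraftment, overall mortality, and non-relapse mortality". Neither names a comparator.

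The section on the clinical impact of DNAemia lists three comparisons. The first is "Patients with DNAemia before engraftment vs after engraftment". The second splits pre-engraftment episodes by whether they began before or after the cell infusion. The third compares pre-engraftment episodes by week of onset. The outcomes listed there are time to engraftment and overall mortality; non-relapse mortality (NRM) is not among them.

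The Statistical Plans section says "CMV DNAemia, CMV DNAemia requiring pre-emptive therapy and CMV-D will be treated as time-dependent co-variates". It describes early and late DNAemia as separate terms: "If either, early or late CMV DNAemia (included individually as time-dependent covariates) are found to have an impact on OS in the univariate analysis", a semi-landmark plot follows. The multivariable Cox model for mortality is built "with inclusion of those variables with a P value less than 0.1 in the prior univariate testing". NRM is to be estimated by cumulative incidence with relapse as the competing event, but the section does not say whether the Cox model for mortality also covers NRM.

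The Study Design section says the study will "include all consecutive allo-HSCT recipients at risk of CMV infection", so DNAemia-free patients are in the cohort.

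**The concern.** A claim of no impact is most naturally a claim about early DNAemia against its absence. Early against late is a legitimate question, but a different one: if both were equally harmful, that comparison would show no difference and could be read as no impact.

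The one place where DNAemia-free patients meet early DNAemia specifically is the univariate model with the early term alone. On the natural reading of that text, its reference is everyone without early DNAemia at that time, including patients who have since had late DNAemia. If late DNAemia raises mortality, the reference is too sick. A real early harm is then understated and may be dropped at the P<0.1 screen before any model with a clean reference is fitted. A truly neutral early effect can look protective. Where late DNAemia is harmful, the error favors the study's own hypothesis, and the Background ties the answer to when prophylaxis should begin.

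**Working it through.** **Inputs from the documents.** The earlier single-center series reports that "a total 38 out of the 197 patients in our series developed CMV DNAemia before engraftment": 38/197 = 19.3%, which agrees with the stated 19%. The number of subjects is 878, given without a derivation, so there is no power figure to reproduce.

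**Assumed inputs (not in the documents).** Late DNAemia in 30%, 50% or 70% of patients without early DNAemia; early onset uniform over days 0–20 and late onset over days 20–100; baseline one-year survival 70%; hazard multiplied by the stated ratio from onset; 365 days of follow-up.

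**Approximate formula.** Let f be the share of the reference person-time that follows late onset. Then

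HR(early alone) ≈ HR_early / [(1 − f) + f × HR_late].

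The assumed late frequencies give f of about 0.23, 0.38 and 0.54. With both true ratios at 1.5:

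- f = 0.23: 1.5 / (0.77 + 0.345) = 1.5 / 1.115 = 1.35
- f = 0.38: 1.5 / (0.62 + 0.57) = 1.5 / 1.19 = 1.26
- f = 0.54: 1.5 / (0.46 + 0.81) = 1.5 / 1.27 = 1.18

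**Simulated hazard ratios.** Counting-process Cox models on 600,000 patients per scenario agree with the formula to within about 0.02:

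| True early HR | True late HR | Early alone, late 30% / 50% / 70% |
|---|---|---|
| 1.5 | 1.5 | 1.35 / 1.26 / 1.17 |
| 1.5 | 2.0 | 1.22 / 1.08 / 0.97 |
| 1.0 | 1.5 | 0.90 / 0.83 / 0.78 |
| 1.5 | 1.0 | 1.50 / 1.50 / 1.49 |
| 1.5 | 0.8 | 1.57 / 1.63 / 1.70 |

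With early and late in one model, the early ratio is 1.48–1.51 where the truth is 1.5, and 1.00 where the truth is 1.0.

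**The P<0.1 screen at 878 patients** (2,000 replicates per scenario; about 1,000 in the last two rows):

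| True early / late HR | Early passes alone | Early P<0.1 in joint model |
|---|---|---|
| 1.5 / 1.5 | 66% / 50% / 32% | 86% / 83% / 79% |
| 1.5 / 2.0 | 44% / 17% / 10% | 86% / 83% / 79% |
| 1.5 / 1.0 | 87% / 87% / 88% | 86% / 81% / 81% |
| 1.5 / 0.8 | 94% / 95% / 97% | 87% / 82% / 77% |

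Both terms pass, so that the plan's own rule yields a joint model, in 42% / 30% / 12% of studies in the first row and 44% / 17% / 9% in the second.

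**A second set of assumptions.** With late DNAemia in 30–55% of all patients and early onset from day −7 (onsets before day 0 counted from day 0), both ratios at 1.5 give an early-alone ratio of 1.20–1.30. At 878 patients with 45% late, power for early at two-sided 0.05 is 32% alone against 73% jointly. With early null and late 1.5, early is significant in 24% of studies alone against 6% jointly.

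**Does the pooled DNAemia covariate rescue the plan?** It has a DNAemia-free reference but mixes early and late. At 30% late, its hazard ratio is 1.24 both when early is 1.5 and late 1.0, and when early is 1.0 and late 1.5. It cannot tell the two apart.

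**The case against.** The comparator is inferred. The hypothesis names none, and the Background dwells on early against post-engraftment episodes. DNAemia-free patients do sit in the reference of the early-alone model, mixed with others, so the analysis is contaminated rather than absent. The key words come from a sentence whose purpose is to trigger a plot, and entering the terms individually could mean two separate covariates in one model. These points justify saying that no analysis *reliably* makes the comparison. They do not remove the problem: the same sentence places the terms in the univariate analysis, and the only stated route to a joint model runs through the screen.

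The loss of power is conditional. If late DNAemia is neutral or protective, the early term passes the screen at least as often as in the joint model (in the protective case because of upward bias). The documents give no late-against-none estimate; the earlier series reports only no significant mortality difference between pre- and post-engraftment DNAemia. This stands, and the sizes above are illustrative.

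The joint model is not a complete cure. Patients who engraft late have longer to be classed as early, and the simulations leave engraftment time unrelated to mortality. A three-level covariate also cannot serve time to engraftment, because post-engraftment DNAemia cannot precede that event. Both limits stand. For engraftment, the listed early-against-late comparison defines its comparison group by having already engrafted, and no regression model is stated.

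**Conclusion.** The concern holds. The plan does not name the contrast that its hypothesis needs, and the nearest stated model has a mixed reference. Over the assumed late frequencies, a true early ratio of 1.5 is estimated at 1.17–1.35 if late is also 1.5, and at 0.97–1.22 if late is 2.0. A null early effect is estimated at 0.78–0.90 if late is 1.5. Direction depends on late DNAemia: downward if harmful, none if neutral, upward if protective. Even with no bias, the missing contrast should be named. The mismatch over NRM, which is in Objective 2 and the hypothesis but not in the clinical-impact list, is a smaller, separate gap. This should be fixed before analysis.

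**What to change.** - Prespecify one Cox model for overall survival with a three-level time-dependent covariate: no DNAemia so far (reference), first DNAemia before engraftment, first DNAemia after engraftment.
- Keep that covariate regardless of its univariate P value; apply the P<0.1 screen only to adjustment variables.
- Report early against none, with its confidence interval, as the main contrast. Report late against none and early against late as secondary.
- Fit the same covariate in a cause-specific Cox model for NRM with relapse as the competing event, and add NRM to the clinical-impact outcomes.
- For time to engraftment, state a separate time-dependent model comparing DNAemia with none so far.

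The cost is plan wording. The data and software are unchanged, and DNAemia-free patients are already in the cohort.
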